## Female participants:

- 9. A female participant is eligible to participate if she is not pregnant or breastfeeding, and at least one of the following conditions applies:
  - Is not a WOCBP

#### OR

• Is a WOCBP and using a contraceptive method that is highly effective (with a failure rate of <1% per year), with low user dependency, or be abstinent from heterosexual intercourse as their preferred and usual lifestyle (abstinent on a long-term and persistent basis), as described in Appendix [5] during the intervention period and for at least 120 days after the last dose of study intervention and agrees not to donate eggs (ova, oocytes) to others or freeze/store for her own use for the purpose of reproduction during this period. The investigator should evaluate the

**Protocol/Amendment No.:** 001-08

potential for contraceptive method failure (ie, noncompliance, recently initiated) in relationship to the first dose of study intervention.

- A WOCBP must have a negative highly sensitive pregnancy test ([urine or serum] as required by local regulations) within 24 hours before the first dose of study intervention.
- If a urine test cannot be confirmed as negative (eg, an ambiguous result), a serum pregnancy test is required. In such cases, the participant must be excluded from participation if the serum pregnancy result is positive.
- The investigator is responsible for review of medical history, menstrual history, and recent sexual activity to decrease the risk for inclusion of a woman with an early undetected pregnancy.
- Contraceptive use by women should be consistent with local regulations regarding the methods of contraception for those participating in clinical studies.

#### **Informed Consent**

10. The participant (or legally acceptable representative if applicable) provides written informed consent for the trial. The participant may also provide consent for FBR. However, the participant may consent to the main trial without participating in FBR.

#### **Additional Criteria**

- 11. HIV-infected participants must meet these additional criteria:
  - a) Have HIV-1 infection documented by any licensed rapid HIV test or HIV E/CIA test kit at any time prior to study entry (Day 1) and confirmed by a licensed Western blot or a second antibody test by a method other than the initial rapid HIV and/or E/CIA, or by HIV-1 p24 antigen, or plasma HIV-1 RNA VL.
  - b) Have well-controlled HIV on antiretroviral therapy (ART), defined as:
    - 1) must have a CD4+ T-cell count >350 cells/mm^3 at time of screening;
    - 2) must have achieved and maintained virologic suppression defined as confirmed HIV RNA level below 50 or the LLOQ (below the limit of detection) using the locally available assay at the time of screening and for at least 12 weeks prior to screening;
    - 3) must have been on a stable regimen, without changes in drugs or dose modification, for at least 4 weeks prior to study entry (Day 1).

**Protocol/Amendment No.:** 001-08

If temporary ART treatment interruptions are required, sponsor consultation is warranted to determine whether the patient can remain on the study or requires discontinuation. These interruptions should not result in poor disease control (eg, significant CD4 count decrease, uncontrolled viremia).

## 6.1.4 Inclusion Criteria for Arm 4 – Subcutaneous Injection

In order to be eligible for Arm 4 of this trial, the participant must:

- 1. Have any histologically or cytologically confirmed advanced/metastatic solid tumor by pathology report and have received, or have been intolerant to, all treatment known to confer clinical benefit. Solid tumors and lymphomas of any type are eligible for enrollment. For CTCL, histopathological diagnosis should be confirmed in a skin biopsy representative of disease [Olsen, E., et al 2007].
- 2. Have Stage III or Stage IV disease that is not surgically resectable. Stage IIB (T3N0M0B0 1) CTCL participants are eligible [Olsen, E., et al 2007].
- 3. Have measurable disease by RECIST 1.1 criteria for solid tumors or revised IWG revised criteria for lymphomas as assessed by the local site investigator/radiology. Lesions situated in a previously irradiated area are considered measurable if progression has been demonstrated in such lesions.
- 4. Have one or more discrete malignant lesions that are amenable to a minimum of three separate biopsies guided by one of the following modalities: visual inspection, ultrasound guidance, or cross-sectional image guidance (computed tomography/magnetic resonance imaging [CT/MRI]).

Note: Participants should only be enrolled if during the screening assessment the investigator deems the biopsy of such lesions to be medically safe.

- 5. Have an ECOG Performance Status of 0 or 1.
- 6. Demonstrate adequate organ function as defined by Table 6.

All screening labs should be performed within 7 days of treatment initiation, unless otherwise specified.

#### **Demographics**

7. Be  $\geq$ 18 years of age on day of signing informed consent.

**Protocol/Amendment No.:** 001-08

# Male Participants:

8. Male participants are eligible to participate if they agree to the following during the intervention period and for at least 120 days after the last dose of study intervention:

• Refrain from donating sperm

#### PLUS either:

• Be abstinent from heterosexual intercourse as their preferred and usual lifestyle (abstinent on a long-term and persistent basis) and agree to remain abstinent

## OR

- Must agree to use contraception unless confirmed to be azoospermic (vasectomized or secondary to medical cause [Appendix 5]) as detailed below:
  - Agree to use a male condom plus partner use of an additional contraceptive method when having penile-vaginal intercourse with a WOCBP who is not currently pregnant. Note: Men with a pregnant or breastfeeding partner must agree to remain abstinent from penile-vaginal intercourse or use a male condom during each episode of penile-vaginal penetration.
- Contraceptive use by men should be consistent with local regulations regarding the methods of contraception for those participating in clinical studies.

## Female Participants:

- 9. A female participant is eligible to participate if she is not pregnant or breastfeeding, and at least one of the following conditions applies:
  - Is not a WOCBP

#### OR

• Is a WOCBP and using a contraceptive method that is highly effective (with a failure rate of <1% per year), with low user dependency, or be abstinent from heterosexual intercourse as their preferred and usual lifestyle (abstinent on a long-term and persistent basis), as described in Appendix [5] during the intervention period and for at least 120 days after the last dose of study intervention and agrees not to donate eggs (ova, oocytes) to others or freeze/store for her own use for the purpose of reproduction during this period. The investigator should evaluate the potential for contraceptive method failure (ie, noncompliance, recently initiated) in relationship to the first dose of study intervention.

**Protocol/Amendment No.:** 001-08

• A WOCBP must have a negative highly sensitive pregnancy test ([urine or serum] as required by local regulations) within 24 hours before the first dose of study intervention.

- If a urine test cannot be confirmed as negative (eg, an ambiguous result), a serum pregnancy test is required. In such cases, the participant must be excluded from participation if the serum pregnancy result is positive.
- The investigator is responsible for review of medical history, menstrual history, and recent sexual activity to decrease the risk for inclusion of a woman with an early undetected pregnancy.
- Contraceptive use by women should be consistent with local regulations regarding the methods of contraception for those participating in clinical studies.

#### Additional Criteria

- 10. HIV-infected participants must meet these additional criteria:
  - a) Have HIV-1 infection documented by any licensed rapid HIV test or HIV enzyme or chemiluminescence immunoassay (E/CIA) test kit at any time prior to study entry (Day 1) and confirmed by a licensed Western blot or a second antibody test by a method other than the initial rapid HIV and/or E/CIA, or by HIV-1 p24 antigen, or plasma HIV-1 RNA VL.
  - b) Have well-controlled HIV on antiretroviral therapy (ART), defined as:
    - 1) must have a CD4+ T-cell count >350 cells/mm^3 at time of screening;
    - 2) must have achieved and maintained virologic suppression defined as confirmed HIV RNA level below 50 or the LLOQ (below the limit of detection) using the locally available assay at the time of screening and for at least 12 weeks prior to screening;
    - 3) must have been on a stable regimen, without changes in drugs or dose modification, for at least 4 weeks prior to study entry (Day 1).

If temporary ART treatment interruptions are required, sponsor consultation is warranted to determine whether the patient can remain on the study or requires discontinuation. These interruptions should not result in poor disease control (eg, significant CD4 count decrease, uncontrolled viremia).

**Protocol/Amendment No.:** 001-08

## 6.2 Exclusion Criteria

Participants are excluded from the study if any of the following criteria apply:

#### **6.2.1** Exclusion Criteria for Initial Treatment

#### **Medical Conditions**

1. Has a history of a second malignancy, unless potentially curative treatment has been completed, with no evidence of malignancy for 2 years.

**Note:** The time requirement does not apply to participants who underwent successful definitive resection of basal cell carcinoma of the skin, superficial bladder cancer, or in situ cervical cancer.

- 2. Has clinically active central nervous system metastases and/or carcinomatous meningitis. Participants with previously treated brain or meningeal metastases may participate and be eligible for treatment provided they are stable and asymptomatic (without evidence of progression by MRI scan of the brain separated by at least 4 weeks after treatment), have no evidence of new or enlarging brain metastases, are evaluated within 4 weeks prior to first study drug administration, and are off immunosuppressive doses of systemic steroids at least 2 weeks from enrollment.
- 3. Has had a severe hypersensitivity reaction to treatment with a monoclonal antibody.
- 4. Has an active autoimmune disease that has required systemic treatment in the past 2 years (ie, with use of disease modifying agents, corticosteroids or immunosuppressive drugs) except vitiligo or resolved childhood asthma/atopy. Replacement therapy, such as thyroxine, insulin, or physiologic corticosteroid replacement therapy for adrenal or pituitary insufficiency, is not considered a form of systemic treatment.
- 5. Has a history of vasculitis.
- 6. Has an active infection requiring therapy.
- 7. Has a history of (noninfectious) pneumonitis that required steroids or current pneumonitis.
- 8. Has undergone prior allogeneic hematopoietic stem cell transplantation within the last 5 years.

**Note:** Participants who have had a stem cell transplant greater than 5 years ago are eligible as long as there are no symptoms of GVHD.

**Protocol/Amendment No.:** 001-08

9. Participants with known Hepatitis B or C infections or known to be positive for HBsAg/ HBV DNA or Hep C Ab or RNA. Active HCV is defined by a known positive Hep C Ab result and known quantitative HCV RNA results greater than the lower limits of detection of the assay.

- 10. Has a history or current evidence of any condition, therapy, or laboratory abnormality that might confound the results of the study, interfere with the participant's compliance for the full duration of the study, would make administration of the study drugs hazardous or make it difficult to monitor adverse effects such that it is not in the best interest of the participant to be enrolled, in the opinion of the treating investigator.
- 11. Has known psychiatric or substance abuse disorders that would interfere in cooperation with the requirements of the trial.
- 12. Is pregnant or breastfeeding or expecting to conceive or father children within the projected duration of the study.
- 13. Has not fully recovered from any effects of major surgery and is free of significant detectable infection. Surgeries that required general anesthesia must be completed at least 2 weeks before first study drug administration. Surgery requiring regional/epidural anesthesia must be completed at least 72 hours before first study drug administration and participants should be recovered.
- 14. HIV-infected participants with history of Kaposi's sarcoma and/or multicentric Castleman's disease
- 15. HIV-infected participants who have had an HIV-related opportunistic infection within 6 months
- 16. Drug-drug interactions have to be taken into consideration and decisions whether a particular drug can be used as a concomitant medication in the study should be based on recommendations at the time of the study and depending on MOA of study drug. Patients on ART agents with a potentially significant overlapping toxicity profile should be excluded if the therapy cannot be switched to the regimen without overlapping toxicity.

# **Prior/Concomitant Therapy**

17. Has had chemotherapy, definitive radiation, or biological cancer therapy within 4 weeks (2 weeks for palliative radiation) prior to the first dose of study therapy, or has not recovered to baseline or CTCAE Grade 1 (Grade 2 alopecia is allowed) from the AEs due to cancer therapeutics administered more than 4 weeks earlier.

**Protocol/Amendment No.:** 001-08

18. Has been treated within 2 weeks of Cycle 1 Day1 with any of the following:

- strong/moderate CYP2C9 inhibitors, such as: amiodarone, felbamate, fluconazole, miconazole, piperine, oxandrolone, fluorouracil and its derivatives (TS-1, UFT, tegafur, carmofur, doxifluridine, capecitabine), sulfaphenazole, cyclosporine, bucurol, and tienilic acid.
- UGT1A3 inhibitors, which include ritonavir, quinidine, probenecid, and valproic acid.
- strong CBR inhibitors, which include quercetin, menadione, glycyrrhetinic acid, and flufenamic acid.
- 19. Is currently participating and receiving study therapy or has participated in a study of an investigational agent and has received study therapy or has used an investigational device within 28 days of administration of MK-2118.

**Note:** Prior exposure to immunotherapeutics is allowed, including PD-1 and PD-L1 inhibitors, provided participant did not experience ≥ Grade 3 drug-related toxicity on monotherapy with a PD-1 or PD-L1 inhibitor.

- 20. Is expected to require any other form of antineoplastic therapy while on study.
- 21. Is on chronic systemic steroid therapy in excess of replacement doses (prednisone ≤ 10 mg/day is acceptable), or on any other form of immunosuppressive medication. For CTCL, continued use of either prednisone ≤ 10 mg/day or continued use of topical steroids is acceptable.

**Note:** The use of physiologic replacement doses of corticosteroids may be approved after consultation with the Sponsor Medical Monitor or designee.

- 22. Has received a live vaccine within 28 days prior to first dose.
- 23. Has been treated with a STING agonist (eg, MK-1454, ADU-S100).
- 24. Has a history of re-irradiation for HNSCC at the projected injection site.

#### 6.2.2 Exclusion Criteria for Crossover into Arm 2

The participant must be excluded from crossover into Arm 2 of the trial if the participant:

#### **Medical Conditions**

1. Has clinically active central nervous system metastases and/or carcinomatous meningitis. Participants with previously treated brain or meningeal metastases may participate and be eligible for treatment provided they are stable and asymptomatic (without evidence of progression by MRI scan of the brain separated by at least

**Protocol/Amendment No.:** 001-08

4 weeks after treatment), have no evidence of new or enlarging brain metastases, are evaluated within 4 weeks prior to first study drug administration, and are off immunosuppressive doses of systemic steroids at least 2 weeks from enrollment.

- 2. Has had a severe hypersensitivity reaction to treatment with a monoclonal antibody.
- 3. Has an active infection requiring therapy.
- 4. Has a history of (noninfectious) pneumonitis that required steroids or current pneumonitis.
- 5. Has a history or current evidence of any condition, therapy, or laboratory abnormality that might confound the results of the study, interfere with the participant's compliance for the full duration of the study, would make administration of the study drugs hazardous or make it difficult to monitor adverse effects such that it is not in the best interest of the participant to be enrolled, in the opinion of the treating investigator.
- 6. Is pregnant or breastfeeding or expecting to conceive or father children within the projected duration of the study.
- 7. Has not fully recovered from any effects of major surgery and is free of significant detectable infection. Surgeries that required general anesthesia must be completed at least 2 weeks before first study drug administration. Surgery requiring regional/epidural anesthesia must be completed at least 72 hours before first study drug administration and participants should be recovered.
- 8. Has a tumor(s) in direct contact or encases a major blood vessel and has ulceration and/or fungation onto the skin surface at the projected injection site.

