#### Type of Participant and Disease Characteristics

- 1. Have any histologically or cytologically confirmed advanced/metastatic solid tumor by pathology report and have received, or have been intolerant to, all treatment known to confer clinical benefit. Solid tumors and lymphomas of any type are eligible for enrollment. For CTCL, histopathological diagnosis should be confirmed in a skin biopsy representative of disease [Olsen, E., et al 2007].
- 2. Have Stage III or Stage IV disease that is not surgically resectable. Stage IIB (T3N0M0B0 1) CTCL participants are eligible [Olsen, E., et al 2007].

**Protocol/Amendment No.:** 001-08

3. Have at least 1 injectable lesion that is amenable to injection and biopsy. Biopsy may be performed via visual inspection or ultrasound guidance. IT injection for cutaneous lesions may be performed via visual inspection. IT injection for subcutaneous lesions may be performed via ultrasound guidance or via palpation. This injectable lesion must be measurable and meet one of the following criteria:

- A cutaneous or subcutaneous lesion ≥1 cm in longest diameter for solid tumors, or ≥1.5 cm in short axis for a nodal lesion in participants with solid tumor. The longest diameter for an injectable lesion must be ≤10 cm for both solid tumors and nodal lesions in participants with solid tumor.
- Multiple coalescing, superficial lesions that in aggregate have a longest diameter of ≥1 cm and ≤10 cm.
- For lymphoma, a nodal lesion ≥1.5 cm in short axis, or an extranodal lesion ≥1 cm in 2 dimensions. Nodal lesions ≥1.0 cm and <1.5 cm in the short axis may be injected, if involvement by lymphoma has been documented by pathology report. The longest diameter for an injectable lesion must be ≤10 cm.
- 4. Have at least 1 discrete and/or distant noninjected lesion that is amenable to biopsy via visual inspection or amenable to biopsy via image guidance. This lesion must be measurable as defined by the response criteria used to assess the participant (RECIST 1.1 for solid tumors or revised IWG criteria for lymphomas).
  - For RECIST 1.1,  $\ge$ 1 cm in longest diameter for nonnodal lesions, or  $\ge$ 1.5 cm in the short axis for nodal lesions.
  - For revised IWG, a nodal lesion >1.5 cm in longest diameter or >1.0 cm in short axis, or an extranodal lesion >1 cm in 2 dimensions.
- 5. Have an ECOG Performance Status of 0 or 1.

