## Type of Participant and Disease Characteristics

In order to be eligible for crossover into Arm 2 of this trial, the participant must:

1. Have either clinical or radiographic disease progression, or progression by global response score for CTCL on Arm 1 MK-2118 monotherapy.

**Protocol/Amendment No.:** 001-08

2. Have completed the DLT evaluation period (21 days of treatment within Cycle 1) in Arm 1 MK-2118 monotherapy.

- 3. Have at least 1 injectable lesion that is amenable to injection and biopsy via visual inspection for a cutaneous lesion, or via ultrasound guidance for a subcutaneous lesion. This injectable lesion must be measurable and meet one of the following criteria:
  - A cutaneous or subcutaneous lesion ≥1 cm in longest diameter for solid tumors, or ≥1.5 cm in short axis for a nodal lesion in solid tumor participants. The longest diameter for an injectable lesion must be ≤10 cm for both solid tumors and nodal lesions in solid tumor participants.
  - Multiple coalescing, superficial lesions that in aggregate have a longest diameter of >1 cm and <10 cm.

  - For lymphoma, a nodal lesion ≥1.5 cm in short axis, or an extranodal lesion ≥1 cm in 2 dimensions. Nodal lesions ≥1.0 cm and <1.5 cm in the short axis may be injected, if involvement by lymphoma has been documented by pathology report. The longest diameter for an injectable lesion must be ≤10 cm.
- 4. Have at least 1 discrete, distant noninjected lesion that is amenable to biopsy via visual inspection or amenable to biopsy via image guidance. This lesion must be measurable as defined by the response criteria used to assess the participant (RECIST 1.1 for solid tumors or IWG revised criteria for lymphomas).
  - For RECIST 1.1,  $\ge$ 1 cm in longest diameter for nonnodal lesions, or  $\ge$ 1.5 cm in the short axis for nodal lesions.
  - For revised IWG, a nodal lesion >1.5 cm in longest diameter or >1.0 cm in short axis, or an extranodal lesion  $\ge 1$  cm in 2 dimensions.
- 5. Have an ECOG Performance Status of 0 or 1.
- 6. Demonstrate adequate organ function as defined by Table 6. All screening labs should be performed within 7 days of treatment initiation.

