## 7.1.1 IT Injection (Arm 1, Arm 2, and Arm 3)

In Arms 1 and 2, MK-2118 will be administered by IT injection into cutaneous, subcutaneous, and/or nodal lesions that are visible, palpable, or detectable by ultrasound guidance.

In Arm 3, MK-2118 will be administered by injection into liver metastasis/lesions by ultrasound or cross-sectional imaging guidance (CT/MRI).

During dose escalation in both Arm 1 and Arm 2, each participant at a given dose level will receive a fixed dose of MK-2118 diluted in a volume of of diluent. See Table 2 and Table 3 for dose level ranges within Arm 1 and Arm 2, respectively. The volume of injectate delivered to each lesion will be based on the longest dimension of the target lesion as shown in Table 8, and on the number of lesions injected [Rehman, H., et al 2016]. Documentation of dose volume administered per lesion will be obtained.

**Protocol/Amendment No.:** 001-08

During dose escalation in Arm 3, each participant at a given dose level will receive a fixed dose of MK-2118 diluted in a volume of of diluent. See Table 4 for dose level ranges within Arm 3. The volume of injectate delivered to each lesion will be based on the longest dimension of the target lesion as shown in Table 9, and on the number of lesions injected.

Regarding prioritization of lesions to be injected at a treatment visit, any new or progressing lesion should be injected first, followed by injection of the largest lesion, with up to a total volume of injectate of 4 mL per treatment visit. Injection of more than one lesion, if feasible, is suggested. See Appendix 7 for further guidance.

For Arms 1 and 2, if there are multiple lesions, then up to a maximum of 8 lesions may be injected per treatment visit, with a minimum injectate volume of 0.5 mL per lesion, and a total injectate volume of 4 mL per treatment visit.

For Arm 3, if there are multiple lesions, then up to a maximum of 4 lesions may be injected per treatment visit, with a minimum injectate volume of 1 mL per lesion, and a total injectate volume of 4 mL per treatment visit.

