#### **Patient Safety**

The first priority is patient safety. Lesions are to be selected that minimize the potential for procedural complications and maximize patient comfort. One important safety factor is vascularity within a lesion, and adjacent to a lesion. Injection into IT vessels should be avoided to minimize systemic administration. Vessels adjacent to a tumor should not be traversed to minimize bleeding risk, and areas of vascular encasement should be avoided in high risk locations (e.g. inferior vena cava encasement for liver lesions, or carotid artery encasement for head and neck tumors).

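### The exclusion for ulcerated or fungating tumors touching a major blood vessel at the injection site applies only to crossovers; new Arm 1 and Arm 2 participants have no explicit equivalent

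*Combined protocol and SAP*

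**What the plan says.** Section 6.2.2 opens by limiting its list to one situation: "The participant must be excluded from crossover into Arm 2 of the trial if the participant" meets any of its items. Item 8 of that list excludes a tumor that is "in direct contact or encases a major blood vessel and has ulceration and/or fungation onto the skin surface at the projected injection site".

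First enrollment is governed by Section 6.2.1, items 1 to 24. Its only criterion tied to the injection site is item 24: "Has a history of re-irradiation for HNSCC at the projected injection site". The crossover list repeats this as item 16.

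For Arms 1 and 2, Section 7.1.1 describes one procedure for new and crossover participants alike: "MK-2118 will be administered by IT injection into cutaneous, subcutaneous, and/or nodal lesions". The lesion requirement for new participants (Section 6.1.1 item 3) begins "Have at least 1 injectable lesion that is amenable to injection and biopsy" and then sets size limits. The crossover version (Section 6.1.2 item 3) begins in nearly the same way: "Have at least 1 injectable lesion that is amenable to injection and biopsy via visual inspection for a cutaneous lesion".

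**The concern.** The hazard in item 8 comes from the lesion and the needle. It does not depend on whether the participant has already received MK-2118. A new participant with such a lesion faces the same injection as a crossover participant, but only the crossover participant is excluded by a written rule.

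The result is also odd in sequence. Every crossover participant first entered Arm 1 under Section 6.2.1. Someone with such a lesion at baseline could have it injected in Arm 1 and then be refused Arm 2 because of it.

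What is at stake is participant safety in a first-in-human trial with repeated dosing: Section 5.1 places Cycle 1 doses on Days 1, 8 and 15. No endpoint, dose-limiting toxicity rule or analysis is affected.

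**Working it through.** The plan states no figure to reproduce. The check is a comparison of the lists, followed by a rough count of the enrollments concerned.

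**1. Matching the two exclusion lists.** Each crossover item (Section 6.2.2) is paired with its counterpart for initial treatment (Section 6.2.1):

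1→2, 2→3, 3→6, 4→7, 5→10, 6→12, 7→13, **8→none**, 9→17, 10→19, 11→20, 12→21, 13→18, 14→22, 15→23, 16→24.

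So 15 of the 16 crossover exclusions have a counterpart, some adapted for earlier MK-2118 exposure. Item 8 is the only one without. Items 1 to 24 of Section 6.2.1 are numbered consecutively with no visible redaction, so a blacked-out item does not explain the gap.

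**2. What each group is covered by.**

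| Provision | New, Arms 1 and 2 | Crossover | Names ulceration or fungation? |
|---|---|---|---|
| Investigator-judgment exclusion | 6.2.1 item 10 | 6.2.2 item 5 | No |
| Injectable-lesion criterion | 6.1.1 item 3 | 6.1.2 item 3 | No |
| Platelet and coagulation limits (Table 6) | 6.1.1 item 6 | 6.1.2 item 6 | No |
| Safety judgment before biopsy | 2.1 note a; 9.7.2 | Same | No |
| Lesion-choice guidance | Appendix 7, through 7.1.1 | Same | No |
| Re-irradiated head and neck cancer | 6.2.1 item 24 | 6.2.2 item 16 | No |
| Vessel involvement plus ulceration or fungation | None | 6.2.2 item 8 | Yes |

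The first six rows apply to both groups. The last is an additional bar that only crossovers have. The sponsor did not treat the general safeguards as sufficient for crossovers, and the protocol gives no reason for treating them as sufficient for new participants.

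**3. Enrollments without the explicit criterion.** Section 10.9 plans about 35 participants in each of Arms 1 and 2. Sections 7.2.2 and 7.3 require at least half of Arm 2 to be MK-2118-naïve in order to establish the maximum tolerated or administered dose.

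- No crossovers in Arm 2: 35 + 35 = 70.
- Half of Arm 2 filled by crossovers: 35 + 35/2 = 52.5, about 53.

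**4. Participants who might have such a lesion.** The documents give no prevalence. Assuming 1% to 5%:

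- Low end: 53 × 0.01 ≈ 0.5.
- High end: 70 × 0.05 = 3.5.

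**The case against.** The strongest reply is that the vessel hazard is already handled lesion by lesion, for everyone injected. Section 7.1.1 points to Appendix 7, which puts patient safety first, advises against injecting into vessels within a tumor or crossing vessels beside it, and says that "areas of vascular encasement should be avoided in high risk locations". New participants must also provide a screening biopsy of the lesion to be injected unless it is medically unsafe, so the investigator has to consider that lesion before the first dose. Section 6.2.1 item 10 further excludes anyone with a condition that "would make administration of the study drugs hazardous or make it difficult to monitor adverse effects".

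This stands in part: injections are not unguarded, and a careful investigator would probably turn away many such lesions. But Appendix 7 is advisory and leaves the choice to clinical judgment, an unsafe biopsy is waived without barring enrollment, and Table 6 makes an exception for participants on therapeutic anticoagulation. Listed criteria are different in kind, because Section 6 forbids prospective waivers.

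A second point is that lesions are chosen again at each visit, so a baseline exclusion would not govern a lesion first selected later. This is correct and limits what the fix achieves, although item 8 has the same limit for crossovers.

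Third, crossovers have progressed on MK-2118, so their lesions may be worse. The protocol does not give this as a reason, and new participants also have advanced disease after exhausting, or not tolerating, beneficial treatment.

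Finally, the 1% to 5% range has no support in the documents, and 70 is a planning figure, not a ceiling. Both points are accepted. The estimate only illustrates scale.

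**Conclusion.** The concern holds. The criterion appears in one of the two exclusion lists, is absent from all 24 items of the other, and no reason is given for the difference. Under the plan as written, a lesion that disqualifies a participant at crossover can be injected in a newly enrolled Arm 1 or Arm 2 participant, subject only to general safeguards.

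This is a gap in explicit eligibility that should be closed, though it is not a critical failing. It concerns roughly 53 to 70 planned enrollments. The number with such a lesion is unknown and probably small, because item 8 is read as requiring both vessel involvement and ulceration or fungation. The figure of 0.5 to 3.5 participants rests entirely on the assumed 1% to 5%. The documents do not clearly say whether Arms 1 and 2 were still enrolling at this amendment. If they had closed, the change would have no practical effect.

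**What to change.** Add the item 8 wording to Section 6.2.1, limited to participants receiving intratumoral injection in Arms 1 and 2. Arm 3 injects liver lesions and Arm 4 has no intratumoral injection, so neither needs it. If the restriction to crossovers was deliberate, the protocol should say why. An explanation alone would document the difference but would not protect new participants.

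The cost is one line in the next amendment and a very small loss of eligible participants, about 0.5 to 3.5 on the same assumption. Screening under Section 2.1 already includes a full physical examination, tumor imaging and photography of cutaneous lesions, so no new procedure is required. Lesions first chosen after baseline would still depend on Appendix 7.
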